8.1.3 Unexpected AE or SAR

An AE or SAR is considered unexpected if the specificity or severity of it is not consistent with the applicable product information (e.g., Investigator's Brochure (IB) for an unapproved investigational product or package insert/summary of product characteristics for an approved product).

Unexpected also refers to AEs or SARs that are mentioned in the IB as occurring with a class of drugs or as anticipated from the pharmacological properties of the drug but are not specifically mentioned as occurring with the particular drug under investigation.

8.1.4 Serious AE or SAR

An AE or SAR is considered serious if, in the view of either the investigator or sponsor, it results in any of the following outcomes:

- Death;
- Is life-threatening (places the subject at immediate risk of death from the event as it occurred);
- Requires inpatient hospitalization (>24 hours) or prolongation of existing hospitalization; *
- Results in congenital anomaly/birth defect;
- Results in a persistent or significant incapacity or substantial disruption of the ability to conduct normal life functions;
- Important medical events that may not result in death, be life-threatening, or require hospitalization may be considered a serious adverse drug experience when, based upon appropriate medical judgment, they may jeopardize the patient or subject and may require medical or surgical intervention to prevent one of the outcomes listed in the definition. For reporting purposes, also consider the occurrences of pregnancy as an event which must be reported as an important medical event.

*Hospitalization for anticipated or protocol specified procedures such as administration of chemotherapy, central line insertion, metastasis interventional therapy, resection of primary tumor, or elective surgery, will not be considered serious adverse events.

Pregnancy that occurs during the study must also be reported as an SAE.

8.2 Documentation of non-serious AEs or SARs

For non-serious AEs or SARs, documentation must begin from day 1 of study treatment and continue through the 30-day follow-up period after treatment is discontinued.

Collected information should be recorded in the Case Report Forms (CRF) for that patient. Please include a description of the event, its severity or toxicity grade, onset and resolved dates (if applicable), and the relationship to the study drug. Documentation should occur at least monthly.

8.3 SAEs or Serious SARs

8.3.1 Timing

After informed consent but prior to initiation of study medications, only SAEs caused by a protocol-mandated intervention will be collected (e.g. SAEs related to invasive procedures such as biopsies, medication washout).

For any other experience or condition that meets the definition of an SAE or a serious SAR, recording of the event must begin from day 1 of study treatment and continue through the 30-day follow-up period after treatment is discontinued.

8.3.2 Documentation and Notification

These events (SAEs or Serious SARs) must be recorded in the SAE console within Oncore™ for that patient within 24 hours of learning of its occurrence.

8.3.3 Reporting

IRB Reporting Requirements:

- The UNC-IRB will be notified of all SAEs that qualify as an Unanticipated Problem as per the UNC IRB Policies using the IRB's web-based reporting system within 7 days of the Investigator becoming aware of the problem.

Pregnancy

Pregnancies and suspected pregnancies (including a positive pregnancy test regardless of age or disease state) of a female subject occurring while the subject is on study should be recorded as SAEs. The patient is to be discontinued immediately from the study. The female subject should be referred to an obstetrician-gynecologist, preferably one experienced in reproductive toxicity for further evaluation and counseling.

The Investigator will follow the female subject until completion of the pregnancy and must document the outcome of the pregnancy (either normal or abnormal outcome). If the outcome of the pregnancy was

abnormal (e.g., spontaneous or therapeutic abortion), the Investigator should report the abnormal outcome as an AE. If the abnormal outcome meets any of the serious criteria, it must be reported as an SAE.

8.3.4 Data and Safety Monitoring Plan

The Principal Investigator will provide continuous monitoring of patient safety in this trial with periodic reporting to the Data and Safety Monitoring Committee (DSMC).

Meetings/teleconferences will be held at a frequency dependent on study accrual, and in consultation with the study Biostatistician. These meetings will include the investigators as well as protocol nurses, clinical research associates, regulatory associates, data managers, biostatisticians, and any other relevant personnel the principal investigators may deem appropriate. At these meetings, the research team will discuss all issues relevant to study progress, including enrollment, safety, regulatory, data collection, etc.

The team will produce summaries or minutes of these meetings. These summaries will be available for inspection when requested by any of the regulatory bodies charged with the safety of human subjects and the integrity of data including, but not limited to, the oversight (Office of Human Research Ethics (OHRE) Biomedical IRB, the Oncology Protocol Review Committee (PRC) or the North Carolina TraCS Institute Data and Safety Monitoring Board (DSMB).

The UNC LCCC Data and Safety Monitoring Committee (DSMC) will review the study on a regular (quarterly to annually) basis, with the frequency of review based on risk and complexity as determined by the UNC Protocol Review Committee. The UNC PI will be responsible for submitting the following information for review: 1) safety and accrual data including the number of study participants treated; 2) significant developments reported in the literature that may affect the safety of participants or the ethics of the study; 3) preliminary response data; and 4) summaries of team meetings that have occurred since the last report. Findings of the DSMC review will be disseminated by memo to the UNC PI, PRC, and the UNC IRB and DSMB.

9.0 STATISTICAL CONSIDERATIONS

This is a nonrandomized, single-center study. The primary purpose and endpoint of this study is to evaluate the sensitivity and specificity of CESR imaging in the analysis of known breast and thyroid lesions by comparing image analyses to the pathological results for these lesions.

9.1 Study Design/Study Endpoints

This is a prospective study to assess the diagnostic performance of the newly developed device. The **primary outcome of interest is the sensitivity and specificity of the super-resolution imaging device in the analysis of known breast and thyroid lesions as compared to pathological results of these lesions**. The sensitivity and specificity can be estimated non-parametrically as the proportion of the lesions which are distinguished as malignant versus non-malignant compared to the reference. This estimate will be calculated for each reader then averaged over all the readers. The standard error of the average sensitivity and specificity estimate will be calculated using the bootstrap method, where each patient is treated as independent unit with 5 ratings. The confidence interval of the final estimate will be provided using the normality assumption.

Furthermore, we will estimate the sensitivity and specificity of the b-mode ultrasound in this study and compare it with the sensitivity and specificity estimate of the CESR imaging using the bootstrap approach and the confidence interval of their differences will be provided using the normality assumption.

Malignancy scores of +1 and +2 will be considered malignant. Scores of -2, -1, and 0 will be considered not malignant. The confidence of malignancy will be used independently

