4.2.5 Reader Study

[figure not shown]
A reader study will be performed after the completion of patient accrual to study lesion characteristics under CESR as compared to conventional b-mode ultrasound. In these pilot observational studies, the primary aim will be to evaluate the imaging approach for application in these two organs. We will also estimate the receiver operating characteristic (ROC) curve for the CESR system. For scientific rigor, a total of five readers who are not investigators on this study (radiologists trained in breast imaging or ultrasound imaging) will be recruited to participate for each reader study. The readers will be asked to assign a probability score (1 to 5) and confidence for each lesion for each modality (0 to 100%). ROC analysis will be performed as the primary analysis for the first aim. To compare the results from the two imaging modalities, we will adopt the mixed effect ANOVA based on the Dorfman-Berbaum-Metz method. The outcome variable is the Tukey's jackknife pseudovalues of the AUCs from each reader and each patient under either modality, and separately for each anatomic region. The fixed effect in the independent list will correspond to the difference between the two modalities, and the random effects will be used to account for within-patient and within-reader's correlations. Possible interactions between the modalities and the readers and the patients will also be included and tested for statistical significance. To test the main hypothesis, F-test statistic from the model parameter estimates will be used to compare the mean AUCs between the b-mode ultrasound images and the CESR ultrasound images only.

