9.2 Data Analysis Plans

ROC analysis will be performed as the primary analysis for the first aim. To compare the results from the two imaging modalities, we will adopt the mixed effect ANOVA based on the Dorfman-Berbaum-Metz method. The outcome variable is the Tukey's jackknife pseudovalues of the AUCs from each reader and each patient under either modality, and separately for each anatomic region. The fixed effect in the independent list will correspond to the difference between the two modalities and the random effects will be used to account for within-patient and within-reader's correlations.

Possible interactions between the modalities and the readers and the patients will also be included and tested for statistical significance. To test the main hypothesis, F-test statistic from the model parameter estimates will be used to compare the mean AUCs between the b-mode ultrasound images and the CESR ultrasound images only.

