9.3 Sample Size Considerations in ROC Analysis

For each lesion type, we assume 8 malignant and 7 benign and the AUC for conventional imaging to be 0.7 based on our previous breast studies. We will recruit patients with high TIRADS risk scores (4c, moderately

suspicious and 5, high risk), that have an anticipated risk range of a 50% to in excess of 85%, which will provide an estimated relative risk of 75% to be congruent with the breast population. The power to detect 0.2 AUC difference is about 30%. However, our primary goal is to evaluate the technical ability of the CESR approach to examine lesions in each of these superficial anatomic regions. We will also be evaluating the number of vessels visualized, the effects of respiratory motion and radiologist confidence in interpreting the CESR microvascular images. These studies will guide further development of the imaging approach for a prospective trial.

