9.4 Secondary Analyses

Radiologist Preference

The secondary analysis will be to evaluate reader preference for specific lesion characteristics. To assess the reader preference for modality for each characteristic including shape, margins and vascularity, we will fit a random effect model with only intercept and random terms for patients and readers while the outcomes are the confidence scores (-3 to +3). By testing the intercept significantly larger than zero, we will conclude that the new modality provides more confidence for readers than the conventional one.

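### The bootstrap in 9.1 resamples patients only, so the standard error of reader-averaged sensitivity and specificity omits the between-reader main effect, although 9.2 and 9.4 treat the same readers as random

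*Combined protocol and SAP*

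**What the plan says.** Section 9.1 names sensitivity and specificity of CESR against pathology as the primary outcome. On the point estimate it says: "This estimate will be calculated for each reader then averaged over all the readers". On precision, it takes the standard error of that average from a bootstrap "where each patient is treated as independent unit with 5 ratings". On the interval: "The confidence interval of the final estimate will be provided using the normality assumption". The CESR minus b-mode differences get a bootstrap and a normal interval as well. Nowhere does 9.1 say that readers are resampled or that a between-reader term is added.

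The other reader-study analyses treat readers differently. In the AUC model of 9.2 (repeated in 4.2.5), "the random effects will be used to account for within-patient and within-reader's correlations", and interactions of modality with readers and patients may be added. For preference, 9.4 states: "we will fit a random effect model with only intercept and random terms for patients and readers".

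Section 4.2.5 recruits "a total of five readers who are not investigators on this study" for each reader study. Section 9.3 gives the lesion counts: "For each lesion type, we assume 8 malignant and 7 benign".

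**The concern.** A bootstrap that resamples patients and keeps their five ratings together conditions on the five radiologists who happened to be recruited. Its interval describes how the average of those five would vary over new patients. It does not describe how the average would vary with a different set of radiologists. The AUC and preference analyses of the same reader study do allow for that, so the endpoint labelled primary is the only one whose inference stops at the five readers, and the plan does not say that this is intended.

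The outcome is described as the performance of the imaging device, and the results are meant to guide a later prospective trial. With stated power of only about 30% for the AUC comparison, the intervals are much of what this study will deliver. If they hold for five readers but are read as the accuracy of the technique, they are too narrow for that use.

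**Working it through.** **1. The plan's own figure.** The only design figure is the power of about 30% for an AUC difference of 0.2 (9.3). Hanley-McNeil standard errors with 8 and 7 lesions are 0.138 at AUC 0.7 and 0.085 at AUC 0.9. With an assumed correlation of 0.3, the SE of the difference is √(0.138² + 0.085² − 2×0.3×0.138×0.085) = 0.139. Two-sided power at 0.05 is then Φ(0.2/0.139 − 1.96) ≈ 30%. The figure is attainable but concerns AUC. The plan gives no standard error, interval width or reader variance for sensitivity or specificity.

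**2. What the bootstrap captures.** With J = 5 readers and n lesions in the relevant pathology group,

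Var(average) = σ²_R/J + σ²_P/n + σ²_RP/(nJ).

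Resampling patients with their ratings estimates the second and third terms. The first, the between-reader main effect, is absent. It sets a floor of σ_R/√5 that more patients cannot lower: 0.022, 0.045, 0.067 and 0.089 for σ_R = 0.05, 0.10, 0.15 and 0.20.

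For CESR minus b-mode the same readers score both modalities. A shared reader effect cancels, and what is omitted is the variance of the reader-specific differences (reader-by-modality) divided by 5.

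**3. Coverage over a reader population (assumed inputs).** Probit reader model, sensitivity 0.75, n = 8, J = 5, latent case variance 0.4 or 0.7 out of 1 before the reader effect is added, 95% normal interval (9.1 states no level).

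| Latent reader SD | SD in sensitivity | Patient-only coverage |
|---|---|---|
| 0 | 0 | 85-87% |
| 0.3 | about 0.09 | 83-84% |
| 0.8 | about 0.21 | 70-72% |

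A crossed reader-by-case variance gives 86-88%.

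**4. A second setting.** Sensitivity 0.80, n = 8, latent case correlation 0.5. SE is the average estimated standard error, without and with the reader term.

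| σ_R | SE | Coverage |
|---|---|---|
| 0.05 | 0.086 → 0.092 | 82.2% → 84.1% |
| 0.10 | 0.083 → 0.096 | 79.8% → 84.1% |
| 0.15 | 0.077 → 0.102 | 74.4% → 82.9% |
| 0.20 | 0.069 → 0.113 | 66.2% → 81.4% |

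Hand check at σ_R = 0.10: a bootstrap variance is low by the factor (n−1)/n, so the true SE is about √(0.083²×8/7 + 0.10²/5) = √(0.00787 + 0.00200) = 0.099. The ratio 0.083/0.099 = 0.84 agrees with the simulation.

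For specificity 0.70 with n = 7, patient-only coverage falls from 85% with no reader variation to 74% at σ_R = 0.20.

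**5. How much is due to readers.** In step 3, readers cost about 2-3 points at latent SD 0.3 and about 13-17 at 0.8. The first 8-10 points below 95% are there with no reader variation at all. They come from a normal interval on very few lesions, including the (n−1)/n shrinkage: √(7/8) = 0.94 and √(6/7) = 0.93 of the true SE.

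**6. Empty pathology groups.** If all 15 patients are resampled together, the chance of drawing no benign lesion is ((15−b)/15)^15 for b benign lesions: 0.008% at the planned 7, 1.0% at 4 and 11.7% at 2. About 4 benign corresponds to the 75% malignancy figure in 9.3 (15×0.25 = 3.75), and about 2 to the 85% end of its range (15×0.15 = 2.25).

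**The case against.** The best defence is that fixed readers are a legitimate choice in a pilot. Section 4.2.5 uses that word, and 9.3 accepts low power and looks ahead to a further trial. If the target is the average accuracy of these five readers, the omission does no harm: coverage at 8 lesions is about 85-87% in the first setting and 82-86% in the second, whatever the reader spread. This stands as an option. It does not describe the current text, which nowhere limits the conclusion and treats readers as random in 9.2 and 9.4.

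The severe end is also assumed. A between-reader SD of 0.21 is wide for trained radiologists applying one cut-off, and at 0.05 the loss is about 2 points. The documents establish the direction of the error but not its size.

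Several stronger readings are tempting and are not supported:

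- A reader might infer that reader variability is ignored altogether. Reader-by-case variation travels with the five ratings and is captured.
- A reader might attribute the whole shortfall from 95% to readers. With no reader variation, coverage is already 85-87% at 8 lesions and 76-77% at 4.
- A reader might assume the differences suffer equally. A shared reader effect cancels there, and the coverage figures above are for a single modality.
- A reader might infer that specificity will often be undefined in the bootstrap. Section 9.1 is silent on stratification, and at the planned 7 benign lesions the event is negligible.

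**Conclusion.** The point holds in a limited form. As written, 9.1 omits reader variance divided by 5 from the standard error of the primary estimates, and reader-by-modality variance from that of the differences. For inference beyond these five readers the intervals are too narrow whenever those variances are not zero, and the primary analysis is inconsistent with 9.2 and 9.4.

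The size depends on a reader variance that the documents do not give. Under the assumptions shown, the loss of coverage due to readers runs from about 2 points when they differ little to about 17 when they differ widely. Adding the reader term recovers most of that loss but does not bring coverage to 95%, because the normal interval on 7-8 lesions is a separate and, at modest reader variation, larger cause. The change should be made. It affects how the primary intervals may be read and leaves the point estimates untouched.

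**What to change.** In 9.1, replace the patient-only bootstrap with a random-reader, random-case variance for the binary sensitivity and specificity, in line with 9.2. Add a reader-by-modality term for the CESR minus b-mode differences, and use a small-sample interval in place of the plain normal one. State the confidence level.

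A two-way bootstrap of readers and patients is acceptable, but it is conservative when readers agree: with no reader variation it gave an SE of 0.114 against a true 0.096.

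If fixed readers are intended, 9.1 should say so, limit the stated conclusion to these five readers and report each reader's result.

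Drawing patients within pathology groups is a harmless addition that matters only if few lesions turn out benign.

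The cost is a few sentences and minor programming, with no new data. The drawback is wider, less favourable intervals.

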1.0 BACKGROUND AND RATIONALE

1.1 Study Synopsis

Increasing the sensitivity and specificity of diagnostic imaging in patients at high risk for breast or thyroid cancer could provide substantial clinical benefit by improving diagnosis, preventing over-treatment, and reducing healthcare costs. Contrast enhanced super-resolution (CESR) imaging is a new type of contrast enhanced ultrasound imaging which is specifically sensitive to microvascular structure and density. It evaluates tumor microvasculature on the order of 10 – 100 microns in diameter and may provide a powerful prognostic tool for the diagnosis of breast cancer, and eventually for treatment evaluation.

This is a 3-arm single center study of 45 patients. These cohorts will include 15 breast patients scheduled to undergo a biopsy, and 15 thyroid patients scheduled to undergo fine needle aspiration, biopsy, or thyroidectomy that consent to undergo CESR imaging in conjunction with b-mode ultrasound prior to their scheduled biopsy. Prior to imaging clinical patients, the third arm will include 15 healthy volunteers that will be imaged to optimize imaging parameters. Despite the similarity to our previous study, LCCC 1748, optimization is required because we will employ a new imaging technique using a different US system. The optimization includes adjusting the frame rate, power, depth of imaging, and the linear translation rate. The primary objectives of this study are to evaluate the sensitivity and specificity of CESR imaging in the analysis of known breast and thyroid lesions by comparing image analyses to the pathological results for these lesions. The secondary objectives of this study are to compare the sensitivity and specificity of CESR imaging with traditional b-mode ultrasound in the distinction of malignant versus benign breast and thyroid lesions.

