1.2 Disease Background

1.2.1 Breast Cancer

Breast cancer is the most common cancer type among women. Approximately 10% of women in the United States develop breast cancer during their lifetime, and 30% to 40% of these patients will die from it.[1, 2] Mammography is an effective tool for the early detection of breast cancer in the majority of women.[3] However, for women with dense breast tissue (considered an independent risk factor for breast cancer) and younger women, mammography performs poorly due to lower sensitivity and specificity in these groups.[4] For young women with heritable mutations who wish to begin screening at a younger age, these limitations are especially problematic.[5] Additionally, mammography is less sensitive in women who have undergone breast augmentation. Given these limitations, most of these women may undergo additional imaging with breast ultrasound or Magnetic Resonance Imaging (MRI).

MRI is time consuming, extraordinarily costly, and has limited availability, especially among rural and underserved populations. Another screening option, breast ultrasound (without contrast), is widely used when additional imaging beyond mammogram is required due to its real-time imaging capability (>30 images per second), portability, safety (does not involve radiation), and relatively low cost compared to breast MRI. Unfortunately, while breast ultrasound is highly sensitive (96%), it is less specific (70%), resulting in a high false positive rate. This results in unnecessary biopsies with associated complications, additional follow-up and negative psychosocial impacts on patients, e.g., significant anxiety. A significant clinical need exists to improve breast ultrasound sensitivity and specificity.

1.2.2 **Thyroid Cancer**

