3.2.1.1 Women ≥ 18 years old

3.2.1.2 Patient had a diagnostic breast ultrasound study performed at UNC

3.2.1.3 Scheduled for a core needle or surgical breast biopsy of at least one breast lesion that is 2 cm or less in size and 3 cm in depth from the skin surface

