3.3 Arm 3: Thyroid Imaging Patients

3.3.1 Inclusion Criteria

Subject must meet all of the inclusion criteria to participate in this study:

- 3.3.1.1 Adults \geq 18 years old
- 3.3.1.2 Patient had a diagnostic thyroid ultrasound study performed at UNC
- 3.3.1.3 TIRADS risk score of 4c or 5
- 3.3.1.4 Scheduled for a core needle or surgical thyroid biopsy, fine needle aspiration, or thyroidectomy of at least one sonographically visible thyroid lesion that is 3 cm in depth from the skin surface
- 3.3.1.5 Lesion visualized on ultrasound
- 3.3.1.6 Able to provide informed consent
- 3.3.1.7 Negative urine pregnancy test in women of child-bearing potential

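### The normal-approximation intervals for sensitivity and specificity in section 9.1 are too narrow at 8 malignant and 7 benign lesions per organ, and collapse to 100-100% when every read is correct

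*Combined protocol and SAP*

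**What the plan says.** Section 9.1 names sensitivity and specificity of CESR against pathology as the primary outcome. Each is a proportion calculated per reader and averaged over readers. The standard error comes from a bootstrap "where each patient is treated as independent unit with 5 ratings", and then "The confidence interval of the final estimate will be provided using the normality assumption". For CESR against b-mode, the plan also bootstraps, and "the confidence interval of their differences will be provided using the normality assumption".

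Section 9.3 gives the denominators: "For each lesion type, we assume 8 malignant and 7 benign and the AUC for conventional imaging to be 0.7". Sections 2.1.1 and 2.1.2 set separate objectives for breast and thyroid, and section 1.1 plans 15 patients in each. Each primary interval therefore rests on 7 or 8 lesions.

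The documents give no confidence level, no small-sample interval, no rule for a zero standard error, and no expected CESR sensitivity or specificity.

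**The concern.** A normal interval on a proportion is least reliable when the sample is small and the proportion is near 1, and a useful diagnostic test would sit there. Five readers do not repair this. They read the same 7 or 8 lesions, so the number of independent units stays at 7 or 8, as the plan's own bootstrap unit recognises. That unit is sound; the fault is the symmetric normal interval placed on it.

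At this size the interval is what tells a reader how little is known. Section 9.3 says the results will guide a prospective trial. Intervals that are too short, most of all when accuracy looks best, would make CESR look better established than it is.

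**Working it through.** **The plan's own figure.** The only computed figure in section 9 is about 30% power for an AUC difference of 0.2. Hanley-McNeil variances for AUC 0.7 and 0.9 with 8 and 7 lesions give 30.2% (two-sided 5%) if the between-modality correlation is assumed to be 0.3, and 23.4% at zero correlation. The figure is reproducible under that assumption, but says nothing about the precision of sensitivity or specificity.

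**Inputs.** From the documents: n = 8 and 7 (section 9.3), five readers (section 4.2.5), patient-level bootstrap and normal interval (section 9.1). Assumed, because the plan is silent: 95% level, five fixed readers, one lesion per patient, the true accuracy, and the reader correlation.

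**Formula.** Let y_i be the share of the five readers who are correct on lesion i, and p the mean of the y_i. The limiting within-class bootstrap standard error is SE = sqrt(sum of (y_i - p)²)/n, and the interval is p ± 1.96 SE.

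**Worked cases, n = 8** (Wilson and exact limits use n = 8):

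| Result | SE | Plan | Wilson | Exact |
|---|---|---|---|---|
| 8/8, all readers | 0 | 100-100% | 68-100% | 63-100% |
| 38 of 40 reads, both errors on one lesion | sqrt(7 × 0.05² + 0.35²)/8 = 0.047 | 86-104% | 61-99.6% | 56-100% |
| 7/8, full agreement | sqrt(0.875 × 0.125/8) = 0.117 | 65-110% | 53-98% | 47-99.7% |

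**Exact coverage at full agreement, true value 0.82.**
- n = 8: the interval contains 0.82 only when 4 to 7 lesions are correct. Coverage = 1 - 0.82⁸ - P(X ≤ 3) = 1 - 0.204 - 0.006 = 78.9%, rounding at the end.
- n = 7: it contains 0.82 only when 4 to 6 are correct. Coverage = 1 - 0.82⁷ - P(X ≤ 3) = 1 - 0.249 - 0.023 = 72.8%.

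**Partial agreement.** This was simulated with a probit model having a lesion effect, 40,000 replicates per cell:

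| True value | n | Reader correlation 0.5-0.8 | Correlation 0-1 |
|---|---|---|---|
| 0.82 | 8 | 78-83% (n = 7 and 8 together) | 79-88% |
| 0.82 | 7 | as above | 73-88% |
| 0.7-0.9 | 7-8 | 66-88% | 52-93% |
| 0.96 | 8 | 55-69% | 28-80% |
| 0.70 | 7 | 85-86% | 85-89% |

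The last two rows use the 96% and 70% that section 1.2.1 quotes for conventional breast ultrasound. They are the only sensitivity and specificity figures in the documents, and they illustrate what would happen if CESR matched them.

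At 0.82 and correlation 0.5-0.8, the upper limit exceeds 100% in 35-64% of trials and the width is zero in 1-6%. At 0.96 with n = 8, the width is zero in 31-45%.

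**Robustness at 0.82.** A literal unstratified bootstrap of 15 patients gives 80-89% (n = 8) and 73-88% (n = 7). A beta-binomial reader model with intraclass correlation 0.2-0.8 gives 74-85%.

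**Difference.** The grid had 7 pairs of true values between 0.7 and 0.9, 5 reader correlations, 2 modality correlations (0 and 0.5) and 2 sample sizes, which makes 140 cells. Coverage was 74-98%, and below 95% in 134 cells. The six exceptions all had perfect reader agreement and equal true accuracy.

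**The case against.** The strongest objection is that the size of the shortfall rests on values the plan does not state. The lowest figures (73% at 0.82, 52% at 0.9, 28% at 0.96) need perfect agreement among five readers, and the 100-100% result is uncommon at moderate agreement. Under-coverage in every single-proportion case refers to true values from 0.70 to 0.96; near 0.60-0.62, with n = 7 and perfect agreement, coverage is about 95%. The 96% and 70% describe conventional breast ultrasound, not CESR, this cohort or thyroid. All of this stands, and the figures should be read as conditional. It does not rescue the method: the zero-width and above-100% results need no model, and 78-83% holds at moderate agreement.

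A second objection is that this is a pilot. Section 4.2.5 says so, section 9.3 makes technical ability the main goal, and section 9.2 calls ROC analysis primary for the first aim. This limits the severity. But sections 9.0 and 9.1 make sensitivity and specificity the primary endpoint.

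Third, the 8/7 split and the analysis by organ may not hold. Pooling the organs (16 and 14 lesions) would give about 88-94% at 0.82, still short, and the separate objectives do not suggest it. The 75% risk in section 9.3 would imply about 11 malignant and 4 benign lesions; specificity coverage at 0.82 would then be about 54-81%. The 8/7 split is the milder case.

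Last, Wilson with patients as n trades under-coverage for over-coverage and wider intervals. That is true, and is set out with the fix.

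**Conclusion.** The concern holds: the interval method is wrong for these counts. With a 95% level, five fixed readers, one lesion per patient and 7 or 8 lesions per class, coverage at a true value of 0.82 is about 73-89%, and it worsens as accuracy rises. The zero-width interval when every read is correct follows directly from section 9.1 and needs no assumption about true accuracy or reader correlation. The difference intervals usually fall short as well.

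This should be fixed before the reader data are analysed. It does not threaten the study: point estimates do not change, no decision depends on the intervals, and the damage is overstated precision in results meant to inform a later trial.

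**What to change.** In section 9.1, replace the normality assumption with an interval that stays within 0-100% and is defined when all reads are correct, and state the confidence level. Possible wording: *a 95% Wilson score interval on the reader-averaged proportion, with n equal to the number of patients (one pre-specified index lesion each) in that pathology class and organ.*

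Patients rather than lesions are used because section 9.1 treats the patient as the unit, while eligibility for breast ("Scheduled for a core needle or surgical breast biopsy of at least one breast lesion") and for thyroid (section 3.3.1) allows more than one lesion. In a stress case of 8 lesions in 4 patients, Wilson covered 84-99% with n = lesions and 92-99.9% with n = patients. Section 9.1 speaks of a proportion of lesions, so an index-lesion rule should be adopted deliberately and before reading. If several lesions per patient are to be analysed, the plan should say so.

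Options at n = 7-8:

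| Interval | Coverage | Mean width (n = 8, 0.82, correlation 0.5-0.8) |
|---|---|---|
| Planned normal | 66-88% (true 0.7-0.9, correlation 0.5-0.8) | 0.31-0.37 |
| Wilson, n = patients | 98-99.7% (same range); can dip to about 89% at some true values under perfect agreement | 0.47 |
| Clopper-Pearson, beta-quantile form | at least 97.5%, even at perfect agreement | 0.55-0.56 |
| Wilson on an effective sample size (between n and 5n), t quantile | 93-99.6% (true 0.7-0.9) | 0.38-0.44 |

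Swapping 1.96 for a t quantile in the present formula is not enough: coverage at 0.82 is 79-94% (n = 8) and 75-95% (n = 7), and the zero-width case remains.

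For the CESR minus b-mode difference, a square-and-add interval built from the two Wilson intervals covered at least 95% in all 140 cells. Its mean width is 0.70-0.77, against 0.27-0.66 for the planned interval (n = 8, correlation 0.5-0.8).

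The cost is SAP wording and a few lines of code, plus the index-lesion decision if that wording is used. No new data are needed. Intervals become wider and, with Wilson or Clopper-Pearson, usually conservative.
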